COMIRB 19-0402

PI: [name]

Version Date: December 6, 2023

SARC Approved 5/8/2019

***Per-oral Pancreatoscopy-guided Lithotripsy vs. Extracorporeal Shock Wave
Lithotripsy For Treating Symptomatic Main Pancreatic Duct Stones in Chronic
Pancreatitis: A Multicenter Randomized Clinical Trial***

Lead Site: University of Colorado

Version Date: December 6, 2023

Table of Contents

Table of Contents.....	2
Synopsis	3
List of Abbreviations	4
Study Protocol.....	5
Research Questions and Hypothesis	5
Basic Design of the Study	7
Sample and Methodology	7
Subject Inclusion and Exclusion Criteria	9
Inclusion Criteria:	9
Exclusion Criteria:	9
Study Steps	10
Screening/Baseline Evaluation	10
Consent	10
Randomization	10
Treatment Regimens	10
Outcome Determination	11
Standard of Care/Research Procedure.....	12
Subject and Study Stopping Criteria.....	12
Data Collection Tool	13
Data Analysis Plan	13
Data and safety monitoring plan.....	14
Definition of AEs, serious AEs, and unanticipated problems	14
Procedures for documentation of adverse events	15
Monitoring of Data	16
Feasibility/Recruitment Plan/Materials	16
Training Plan.....	16

Synopsis

Title	Per-oral Pancreatoscopy-guided Lithotripsy vs. Extracorporeal Shock Wave Lithotripsy in Chronic Pancreatitis: A Multicenter Randomized Clinical Trial
Investigative sites	University of Colorado The Ohio State University Baylor St. Luke's Medical Center Methodist Dallas Medical Center University of Minnesota University Health, San Antonio Indiana University Washington University School of Medicine
Hypothesis	The central hypothesis is that per-oral pancreatoscopy- guided lithotripsy is superior to extracorporeal shock wave lithotripsy in clearance of main pancreatic duct stones, thereby improving pain levels and quality of life in patients with chronic calcific pancreatitis.
Primary Objective	To demonstrate the superiority of per-oral pancreatoscopy over extracorporeal shock wave lithotripsy in clearance of main pancreatic duct stones in patients with chronic pancreatitis. Failure to remove any or all stones with the initial intervention will be an outcome recorded for the study.
Secondary Objective	To demonstrate the effect of stone clearance to reduce pain and opiate use and improve quality of life.
Timeline	Enrollment will be performed over a 24-month time period with follow-up performed at 1, 3, 6, 12, 18, and 24 months after ductal clearance.

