Subjects may withdraw from the study at any time for any reason. Subjects can also be withdrawn from the study at any time at the discretion of the investigators for breach of study protocol or emergence of an exclusion criteria (i.e. pregnancy).

The study can be stopped at any point should the Data Safety Monitoring Board (DSMB) request cessation

of the trial based on any compilation of adverse events or clear demonstration of superiority of one technique. Similarly, should the interim analysis reveal futility in that the study hypothesis is deemed unprovable within the constraints of the study, the study may be stopped. The study will also be stopped once the intended sample size goal is reached and 6-month follow-up has been obtained. Lastly, the study can be stopped should study costs exceed the allotted budget.

8. Data Collection Tool

A comprehensive system has been previously developed at this institution, and will support the data collection and reporting needs of this project which includes:

- (i) streamlining data collection from the participating centers,
- (ii) creating a secure database from which statistical analysis can be performed. Data will be stored at the University of Colorado instance of REDCap15, which resides on a local secure server. Data regarding stone clearance rates and adverse events will be entered by investigators at each center. Using an Application Programming Interface (API), data can be transferred to and from REDCap to SAS software (v.9.3, SAS Institute, Cary, NC) used to export data from REDCap to SAS to conduct analysis. SAS software interfaces seamlessly with REDCap-produced syntax files (i.e. SAS code) and SAS-ready CSV (comma separated variables) data files. Results of these analyses will be imported back into REDCap, using the API, for long-term storage, reference, and further analysis. Access to these data will be controlled by a custom module and all users of the site will be required to log in. No protected health information will be collected or displayed and data stored in our HIPAA compliant serve environment to ensure privacy.

9. Data Analysis Plan

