Statistical Analysis: Comparison of technical success rate, defined as the rate of complete clearance of PD stones, between PPL and ESWL will be performing using the chi-squared test or Fisher's exact test. Secondary outcomes including adverse event (both overall and serious adverse event) rates, procedure length, and number of procedures will be compared using a chi-square test or Fisher's exact test for categorical variables and the Student's t test will for continuous variables. A p value <0.05 will be considered significant. In the primary analysis, all results will be analyzed under an intention-to-treat protocol. A per-protocol (secondary) analysis will also be performed where the technical success will be attributed to the combination of modalities resulting in achieving the primary outcome should cross-over occur.

To identify predictors for technical success, a multivariable logistic regression will be performed incorporating variables that were associated ($p<0.2$) with technical success on univariate analysis.

In terms of secondary outcomes, change in PANQOLI scores, VAS scores, and opiate daily doses will be compared between subjects in the PPL group and ESWL group. Additional outcomes to be measured include stone recurrences and number of chronic pancreatitis-related hospitalizations during the follow-up period. Should cross- over occur, under the primary (intention-to-treat) analysis, the outcomes will be attributed to the initially randomized intervention. In the secondary (per-protocol) analysis, the outcomes will be attributed to the combination of treatments resulting in technical success. A subgroup analysis will also be performed on patients who achieved only partial stone clearance (thus considered a treatment

failure) in the above-mentioned outcomes. Comparisons will be made using a chi-squared test or Fisher's exact test for categorical variables and the Student's t test for continuous variables. Paired t tests will be performed to evaluate individual changes within each arm. A p value <0.05 will be considered significant.

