Power analysis: A large meta-analysis by Moole et al found a complete stone clearance rate of 70% in patients who received ESWL in conjunction with ERCP.¹⁴ In contrast, the largest studies examining pancreatoscopy-guided lithotripsy methods have found complete stone clearance rates ranging from 83-99%.^{6,17} Using a conservative stone clearance rate of 90% for pancreatoscopy- guided lithotripsy, a sample size calculation was performed using a two-sided test with 80% power and significance (α) of 0.05. This demonstrated the need for 124 subjects total, with 62 in each arm. Accounting for an expected dropout rate of 20%, the sample size needed would be a total of 150, or 75 subjects in each arm.

10. Data and safety monitoring plan

A Data and Safety Monitoring Board (DSMB) will be established to monitor the data and safety of this project. A DSMB will be appointed by the study team and will include at a minimum: A senior faculty member clinician with substantial research experience within the Division of Gastroenterology and Hepatology at the University of Colorado who is not involved in the study, and will serve as the group leader, a statistician, and a senior gastroenterologist from a non- participating academic institution. The DSMB will meet every six months. DSMB meetings will be only open to designated DSMB staff and other individuals who have been approved to have access to unblinded data. Any recommendations for alteration or termination for part or all of the trial shall be based on consideration of the accumulating data in the context of totality of evidence. Specific statistical monitoring guidelines for safety and efficacy concerning the primary and secondary endpoints will be developed in cooperation with the DSMB.

10.1 *Definition of AEs, serious AEs, and unanticipated problems*

AEs are defined as any undesired, harmful, or pathological change in a patient as indicated by signs, symptoms, or laboratory changes that occur in association with the use of the trial interventions, whether considered intervention-related or not. This definition includes intercurrent illness or injuries, exacerbation of existing conditions, psychological events, psychosocial events, and AEs as a result of the study intervention. All endoscopic AEs will be defined and classified as recommended by the American Society for Gastrointestinal Endoscopy (ASGE).²⁰

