All serious AEs that occur from initiation of the study to 14 days post final intervention are to be reported immediately (within 24 hours) using the electronic data collection system. All serious AEs will then be immediately relayed to the PIs. The PIs will first review the AEs to: 1) ascertain the seriousness, 2) ascertain the relationship between AE and intervention, 3) verify that all data are complete, and 4) follow-up with the specific site for incomplete data and/or data clarification. The PIs will then submit the AEs to the DSMB, who will then review the AEs to confirm the findings of the PIs.

All AEs from ESWL are ESWL-related. PPL is part of the ERCP procedure. Most AEs in this group will be related to the ERCP procedure itself. A potential rare AE specific to PPL (EHL or LL) is ductal perforation from the lithotripsy fiber and will be noted by the investigator. The investigator will determine the relationship of an AE specific to a lithotripsy device used to fragment the stones.

10.3 *Monitoring of Data*

The DSMB will be responsible for data and safety monitoring. All primary and secondary outcomes as well as data integrity and study progress along with all AEs will be reviewed by the DSMB.

The DSMB will meet at least twice a year to review the data mentioned above. These meetings will every six months.

An interim analysis will be performed at the halfway point of enrollment, which is expected to be at the 75th patient. Should the interim analysis reveal an unexpected accumulation of AEs or a clear superiority of one lithotripsy method over the other, the DSMB may recommend stopping the study, which will be reported to the PIs, IRB and the funding agency.

The DSMB will include at a minimum the following individuals:

- [name]: Gastroenterologist, University of Colorado
- [name]: Hepatologist, University of Colorado
- Biostatistician: Non-study Statistician
- [name]: Gastroenterologist, Beth Israel Deaconess Medical Center

11. Feasibility/Recruitment Plan/Materials

The power analysis suggests that a total of 150 participants will need to be enrolled to achieve sufficient statistical power to compare the two lithotripsy methods. With a total of 8 recruitment sites, we anticipate complete enrollment within 5 years and with a follow-up of 12 months/patient post completion of treatment, the study is anticipated to be completed within 6 years.

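### Admissions for chronic pancreatitis would by default be compared as raw counts, although time observed differs between patients; a rate model with a follow-up offset is better (minor)

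*Combined protocol and SAP*

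**What the plan says.** Section 9 (Data Analysis Plan) adds to the secondary outcomes the "number of chronic pancreatitis-related hospitalizations during the follow-up period". The rule for comparing the arms is generic: "Comparisons will be made using a chi-squared test or Fisher's exact test for categorical variables and the Student's t test for continuous variables". The threshold is also generic: "A p value <0.05 will be considered significant". No rate, person-time, count model or fixed counting window appears anywhere in the document.

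The length of follow-up is stated in three ways:

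- Synopsis, Timeline: "follow-up performed at 1, 3, 6, 12, 18, and 24 months after ductal clearance". Section 3 repeats this schedule, starting from complete stone removal.
- Section 7: "The study will also be stopped once the intended sample size goal is reached and 6-month follow-up has been obtained".
- Section 11: "with a follow-up of 12 months/patient post completion of treatment".

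Section 7 also allows withdrawal at any time. The power analysis in Section 9 says "Accounting for an expected dropout rate of 20" percent. Section 3 allows up to four lithotripsy sessions, so the time from randomization to the start of follow-up can vary.

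**The concern.** A patient observed for 6 months with one admission and a patient observed for 24 months with one admission contribute the same value to a t test on counts, although the first has four times the admission rate. This has two consequences.

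If time observed varies between patients but equally in both arms, the extra variation is noise and costs some power. If it differs by arm, the difference in mean counts mixes the admission rate with the time available to be admitted. The second case is possible here because the follow-up clock starts after treatment. If the study closes on a calendar date, the arm with the longer treatment phase has less time in which admissions can be counted. If that arm were ESWL, PPL would look worse than it is, and a true benefit could be hidden.

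**Working it through.** **The plan's own figure.** No sample size or power is given for admissions. The primary calculation reproduces: for 70% vs 90%, two-sided 0.05 and 80% power, n = (1.96·√(2·0.8·0.2) + 0.8416·√(0.7·0.3 + 0.9·0.1))² / 0.2² = (1.109 + 0.461)² / 0.04 ≈ 61.6. That is 62 per arm, 124 in total, as stated. The work below uses the planned 75 per arm.

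**How unequal is follow-up?** Take a 24-month cap, closure 6 months after the last enrolment, uniform accrual, and 20% of patients dropping out at a uniform time. Simulated follow-up is then:

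| Accrual | Mean (SD), months | Reach 24 months |
|---|---|---|
| 24 months (Synopsis) | 15.6 (6.8) | 20% |
| 5 years (Section 11) | 19.2 (6.8) | 56% |

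**Case 1: same follow-up distribution in both arms.** The documents give no admission rate, overdispersion or effect size. Assumed ranges are 0.5 to 1 admission per year, dispersion 0 or 1, and rate ratio 0.5 to 0.7.

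- Type I error of the t test: 4.6 to 5.4%.
- Power, t test vs negative binomial with offset: from 33% vs 33% (24-month accrual, 0.5/year, ratio 0.7, dispersion 0) to 62% vs 69% (5-year accrual, 1/year, ratio 0.7, dispersion 0). The gain is about 0 to 7 points.
- At 0.8/year, dispersion 1, ratio 0.6 and 24-month accrual: 48 to 49% vs 55%.

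**Case 2: follow-up differs by arm.** Assume PPL treatment ends 0.1 years after randomization and ESWL treatment ends at 0.25 or 0.5 years (about 2 or 5 months later). Let the study close when the last possible ESWL patient reaches 6 months. With entry time t uniform over the accrual period and treatment ending at a, potential follow-up is min(cap, closure − a − t). With equal admission rates, the expected count ratio (PPL/ESWL) is the ratio of mean follow-up. Ignoring dropout:

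- 24-month accrual, 5-month lag, closure at 2 + 0.5 + 0.5 = 3.0 years. PPL: 0.45·2 + 0.55·1.45 = 1.70 years. ESWL: 0.25·2 + 0.75·1.25 = 1.44 years. Ratio 1.18.
- 24-month accrual, 2-month lag, closure at 2.75 years. PPL: 0.325·2 + 0.675·1.325 = 1.54. ESWL: 1.44. Ratio 1.07 (about 1.08 in simulation).
- 5-year accrual, 5-month lag, closure at 6.0 years. PPL: 0.78·2 + 0.22·1.45 = 1.88. ESWL: 0.70·2 + 0.30·1.25 = 1.78. Ratio 1.06.
- 12-month cap, 24-month accrual, 5-month lag. PPL: 0.95·1 + 0.05·0.95 = 0.998. ESWL: 0.75·1 + 0.25·0.75 = 0.938. Ratio 1.06.

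Simulation with 0.8 admissions/year, dispersion 1 and dropout of 0.11/year gives:

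| Scenario | t-test error, equal rates | Power at ratio 0.6: t test vs rate model |
|---|---|---|
| 24-month accrual, about 2-month lag | about 6% | about 36% vs 54% |
| 24-month accrual, about 5-month lag | about 9% | about 26% vs 54% |
| 5-year accrual, about 5-month lag | about 5 to 6% | about 42% vs 56 to 60% |

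With a 12-month cap and the 5-month lag, error also stays near 5 to 6%.

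Unequal dropout is another route to the same bias. With 10% vs 30% dropout (also an assumption), mean follow-up differs by about 10%. Error is then 7 to 12% for the t test and 4 to 6% for the rate model.

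**The case against.** The strongest reply has four parts.

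**The t test is not named for this outcome.** That is correct. Section 9 gives generic rules, and "the Student's t test for continuous variables" is the default for a per-patient number because nothing else is offered. Reducing the count to any vs none and using chi-squared would ignore time observed just as much.

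**No document says ESWL treatment lasts longer.** This also stands. Both arms may have up to four sessions, and no interval between sessions or time to completion is given. The protocol describes ESWL as hard to schedule and as needing ERP to remove fragments, which makes a lag plausible but does not size it. A reader might infer a false-positive rate of 12 to 13% and power as low as 18%. Figures of that size need the 5-month lag together with a closure so early that late ESWL patients fall short of 6 months, which does not fit Section 7.

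**On the Section 11 timeline there is little error inflation.** With 5-year accrual, or with 12 months per patient, error stays near 5 to 6%. That stands, although a lag would still cost power. A reader might infer that the t test is invalid under this plan; the documents do not show that.

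**The stakes are low.** Admissions are not among the Synopsis secondary endpoints or the five major secondary endpoints in Section 2. That stands and sets the severity.

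**Conclusion.** The point holds as a minor one. The default analysis ignores time observed, and the plan's own rules make that time unequal between patients. With the same follow-up distribution in both arms, the cost is about 0 to 7 points of power and no loss of error control. Bias arises only if follow-up differs by arm. Its size (count ratio about 1.08 to 1.18 and error about 6 to 9% under 24-month accrual) rests on an assumed treatment lag of 2 to 5 months and on assumed admission rate and dispersion, none of which the documents give. The primary endpoint and its sample size are unaffected.

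**What to change.** In Section 9, replace the t test for this outcome with negative binomial regression of the number of admissions on treatment arm, with log person-time observed as offset, and report the rate ratio with its 95% confidence interval.

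Two things must be settled first, because an offset cannot be computed without them:

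- **Start and end of observation.** Define a start that exists for every randomized patient, including those whose ducts are never cleared; the Synopsis and Section 3 start the clock only at clearance. Randomization to last contact is one option. It also takes treatment length out of the comparison, but it brings treatment-phase admissions into the count, which the plan should say.
- **Length of follow-up.** Reconcile the 6-, 12- and 24-month statements in Section 7, Section 11 and the Synopsis.

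The cost is a few sentences, an admission date for each event and a last-contact date for each patient, and a slightly more complex model. The offset corrects for length of observation; it does not correct for dropout that is itself related to the risk of admission.

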Following baseline assessments and identification of main PD stones, patients will be randomly assigned to receive either PPL or ESWL as the primary lithotripsy method to fracture PD stones. Both these procedures represent potential next steps in the algorithm of managing PD stones.³ If partial clearance (removal of some, but not all stones) of PD stones is achieved as determined by the performing endoscopist, subjects can receive repeated PPL or ESWL sessions (for a maximum of 4 sessions total as is commonly practiced before referral for alternative therapy) until complete removal of stones is achieved.⁵ Failure to remove any main PD stones will be considered a failure of the treatment. Additionally, failure to achieve complete clearance within a maximum of 4 sessions of either PPL or ESWL will be considered a treatment failure, even if partial clearance is achieved.

Cross-over and/or combination therapy will be allowed at the discretion of the endoscopist after treatment failure. As described in the statistical analysis, under the intention-to-treat (primary) analysis, should cross-over occur, the final outcome of complete stone clearance will be attributed to the initial therapy. Under the per-protocol (secondary) analysis, in the case of cross-over, the final outcome of complete stone clearance will be attributed to the combination of ESWL and PPL. Similarly, in terms of survey collection, should cross-over occur, the analysis of the survey results will be attributed to the

originally assigned intervention in the intention-to-treat (primary) analysis. In the per-protocol (secondary) analysis, the outcomes will be attributed to the combination of both interventions resulting in technical success.

Patients who are randomized and subsequently found to have an exclusion criteria identified will continue follow-up per study protocol.

Stone clearance will be determined by occlusion pancreatography showing the absence of main PD stones. Complete stone clearance will be defined as the absence of stones in the head or body of the main PD. Partial stone clearance will be defined as the removal of more than 50% but less than 100% of stone/stone fragments in the head or body of the main PD.

[figure not shown]
Recurrence will be defined as the presence of stones following confirmed clearance in the final pancreatogram. To be considered as recurring, the stone must require intraductal lithotripsy for removal.

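### The partial-clearance subgroup is selected by a result of treatment, so an arm comparison inside it is not protected by randomisation, is very small, and may be biased in an unknown direction

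*Combined protocol and SAP*

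**What the plan says.** Section 9 (Data Analysis Plan) says that changes in PANQOL, VAS and daily opiate dose "will be compared between subjects in the PPL group and ESWL group", and adds stone recurrence and pancreatitis-related hospitalisations as further outcomes. Intention-to-treat is primary. The same paragraph continues: "A subgroup analysis will also be performed on patients who achieved only partial stone clearance", for those same outcomes, and notes that these patients count as treatment failures. The next sentence reads: "Comparisons will be made using a chi-squared test or Fisher's exact test for categorical variables and the Student's t test for continuous variables". After that come within-arm paired t tests and a 0.05 threshold. The subgroup is not called descriptive or exploratory. No expected size, adjustment or caution is given.

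Section 3 (Sample and Methodology) sets the failure rule: "failure to achieve complete clearance within a maximum of 4 sessions of either PPL or ESWL will be considered a treatment failure". It describes partial clearance in two ways: "partial clearance (removal of some, but not all stones) of PD stones", and later "Partial stone clearance will be defined as the removal of more than 50% but less than 100% of stone/stone fragments". It allows cross-over after failure, defines recurrence only after clearance has been confirmed, and times the questionnaires from complete stone removal.

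The power analysis in Section 9 takes a "complete stone clearance rate of 70% in patients who received ESWL in conjunction with ERCP" against 90% for PPL, from a quoted PPL range of 83-99%.

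**The concern.** Membership of the subgroup is decided by how treatment turned out, and the trial is powered on the expectation that this differs by arm. If PPL leaves 10% of patients uncleared and ESWL 30%, the two sets of partial clearers have been selected in different ways. They may differ in stone burden, strictures or disease severity before any effect on pain is considered. Randomisation balances the arms as allocated, not the fractions left after treatment has sorted them.

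At stake is how a p value from this subgroup would be read. A significant result could be taken as the effect of PPL against ESWL after incomplete clearance when it reflects selection. A non-significant one could be taken as reassurance when the sample could detect only a very large difference. Cross-over after failure adds a further difficulty, because later pain and quality-of-life scores in this subgroup may reflect both therapies.

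**Working it through.** **Inputs from the documents.** Complete clearance 70% (ESWL) and 90% (PPL; range 83-99%), two-sided alpha 0.05, power 80%, 62 evaluable and 75 enrolled per arm (Section 9). **Assumptions, because the documents give no figure:** the share of failures that are partial (50-100%), the effect size in SD units, and the link between case difficulty, failure and outcome.

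**1. The plan's own figure.** With pooled variance under the null and mean proportion 0.80:

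n = [1.960 × √(2 × 0.80 × 0.20) + 0.842 × √(0.70 × 0.30 + 0.90 × 0.10)]² / 0.20²
= [1.960 × 0.566 + 0.842 × 0.548]² / 0.04 = 61.6, so 62 per arm and 124 in total.

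This matches the plan. No figure is given for the subgroup.

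**2. Subgroup size.** Expected count = patients per arm × failure rate × share of failures that are partial.

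| Per arm | Share partial | PPL | ESWL |
|---|---|---|---|
| 62 | 100% | 62 × 0.10 = 6.2 | 62 × 0.30 = 18.6 |
| 75 | 100% | 75 × 0.10 = 7.5 | 75 × 0.30 = 22.5 |
| 62 | 50% | 3.1 | 9.3 |
| 75 | 50% | 3.75 | 11.25 |

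The 100% rows are upper bounds, because a patient with no clearance is a failure but not a partial clearer. At 99% PPL clearance fewer than one PPL patient is expected (75 × 0.01 = 0.75).

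**3. Power.** Two-sample t test, noncentral t, noncentrality d × √[n₁n₂/(n₁+n₂)].

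| PPL vs ESWL | Power, 0.5 SD | Power, 1.0 SD | Difference for 80% power |
|---|---|---|---|
| 3 vs 9 | 10% | 27% | 2.07 SD |
| 6 vs 19 | 18% | 53% | 1.37 SD |
| 7 vs 22 | 20% | 60% | 1.26 SD |
| 8 vs 23 | 22% | 65% | 1.19 SD |
| 13 vs 22 (PPL 83%, 75 per arm, all failures partial) | 28% | 79% | 1.01 SD |
| 62 vs 62 (all evaluable patients) | 79% | >99% | 0.51 SD |

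**4. Possible bias with no treatment effect on the outcome.** Suppose one normally distributed ease of clearance ranks patients identically in both arms, and treat all failures as the subgroup. Mean ease among failures is −φ(z_q)/q, where q is the failure rate:

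- q = 0.10: −0.1755/0.10 = −1.75 SD
- q = 0.17: −0.2531/0.17 = −1.49 SD
- q = 0.30: −0.3477/0.30 = −1.16 SD

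Multiplying the gap between arms by an assumed correlation of 0.3-0.5 between ease and outcome:

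- 90% vs 70%: gap 0.596 SD, so 0.18 to 0.30 SD against PPL. In simulation at 75 per arm the nominal 5% test rejects about 7% to 12% of the time.
- 83% vs 70%: gap 0.330 SD, so 0.10 to 0.16 SD against PPL, with rejection about 6% to 8%.

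Relaxing the shared-difficulty assumption changes the answer. If failure is unrelated to difficulty, the bias is zero. If difficulty correlates only 0.3 with PPL failure but 0.8 with ESWL failure, the sign reverses, to between 0.09 and 0.20 SD in favour of PPL (difficulty-outcome correlation 0.5).

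**5. Are the outcomes defined in this subgroup?** Recurrence requires earlier confirmed clearance, which a patient who was never cleared does not have. The 1- to 24-month questionnaires are counted from complete removal, so these patients have no stated time origin. It is also unclear whether having only partial clearance is judged before or after cross-over.

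**The case against.** The strongest objection concerns direction. A reader might infer that PPL's few failures are the hardest cases, that ESWL's are easier, and that the analysis therefore tends to make PPL look worse. The documents make a shared difficulty plausible: both arms end with ERP, and Section 6 says strictures and numerous, large or hard stones make ERP harder. They do not establish it. ESWL also depends on radiographic localisation and targeting (Section 5.4), a different obstacle. The calculation above treats all failures as partial clearers and rests on assumed correlations. This objection stands, so the direction and size of any bias must be left open. It does not rescue the comparison, because a p value whose bias has unknown sign cannot be interpreted either.

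Second, the subgroup sentence never says PPL against ESWL. It could serve the secondary objective on the effect of clearance, and paired within-arm tests are planned in the same paragraph. This stands in part: the between-arm reading is an inference. It is the natural one, since the sentence sits within the arm comparisons and two-sample tests follow directly.

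Third, low power is usual in subgroups, and this is one supplementary analysis. That is correct and limits the severity. Calling the test nearly powerless would also go too far for very large effects, since power at 1.0 SD is 27-65% at the design rates.

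**Conclusion.** The concern holds in limited form. That randomisation does not protect an arm comparison among partial clearers follows from the plan's own definitions and needs no modelling assumption. The small numbers follow from the design rates: at most about 6-8 PPL and 19-23 ESWL patients, power of about 10-22% for 0.5 SD (the low end if half of failures are partial), and 1.2-1.4 SD or more for 80% power. Even the most favourable case in the quoted PPL range gives 28% for 0.5 SD.

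The bias is a possibility, not a finding. It is about 0.2-0.3 SD against PPL at 90% vs 70%, and 0.10-0.16 SD at 83% vs 70%, only if one difficulty scale drives failure in both arms and correlates 0.3-0.5 with outcome. Otherwise it may be zero or reversed. Recurrence and questionnaire timing are not well defined in patients never cleared.

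Severity is low. The primary endpoint and the intention-to-treat secondary comparisons do not depend on this analysis.

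**What to change.** In Section 9, state that patients with only partial clearance will be described by arm, with counts and summary statistics, and without between-arm p values. Omit recurrence for patients who were never cleared. State the time origin for their questionnaires and whether partial status is judged before or after cross-over. Base every arm comparison on all randomised patients, as the intention-to-treat analysis already does. For the p values this is a change of wording, and the only loss is a few that could not be interpreted.

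An ordered outcome of none, partial or complete clearance in all randomised patients (proportional odds or Wilcoxon) is an optional addition. It answers a different question, about clearance and not about pain or quality of life after incomplete clearance. It is also more than a wording change. The two definitions of partial clearance in Section 3 must first be reconciled, since under the stricter one removal of half or less of the stones has no category. The blinded reading in Section 5.5 lists only complete and partial, so a grade for no clearance would have to be added.
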